## Statistical Analysis Plan

of study drug will be used. The summary for FEV1 will also be provided by smoker status.

- Number and percentage of patients with FEV1/FVC < 60% and <70% by visit
- Spirometry data will also be provided to indicate whether specific determinations met American Thoracic Society (ATS) quality criteria. The proportion of DLCO/spirometry data measurements meeting or not meeting ATS quality criteria will be summarized by treatment group and overall. The summary will also be performed for ON state measurements, OFF state measurements, and all measurements, separately. The reasons for not meeting ATS quality criteria will be summarized, as data allow.
- Categories of changes (<-50%, -50% -<-40%, -40% -<-30%, -30% -<-20%, -20% -<-10%, -10% -<-10%, 10% -<20% , 20% -<30% , 30% -<40% , 40% -<50%, >=50%) from baseline for FEV1, FEV, FEV1/FVC ratio and DLCO by visit. The summary for FEV1 will also be provided by smoker status.
- Actual values and change from pre-dose to post-dose time points for each parameter at TV1; percent change for FEV1 and FVC will also be summarized. If a pre-dose value at TV1 is missing, the last available value in OFF state before the first dose of will be used. The summary for FEV1 will also be provided by smoker status.
- Number and percentage of patients with percent of changes (<-50%, -50% -<-40%, -40% -<-30%, -30% -<-20%, -20% -<-10%, -10% -<-10%, 10% -<20% , 20% -<30% , 30% -<40% , 40% -<50%, >=50%) at each post-dose time point at TV1 from pre-dose for FEV1, FVC and FEV1/FVC. The summary for FEV1 will also be provided by smoker status.

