#### 3.4.1. Inclusion Criteria

[CVT-301-004](#) study patients who have met the eligibility criteria for [CVT-301-004](#) and who have completed all [CVT-301-004](#) study visits per protocol without any safety issues that would preclude participation in this study according to the investigator are eligible for participation in this study. Patients who withdrew from the [CVT-301-004](#) study prior to completion, for any reason, are not eligible.

The inclusion criteria listed below are not assessed for the [CVT-301-004](#) study patients. In order to be eligible to enter the study, patients must meet all of the following criteria:

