## Statistical Analysis Plan

### 6. GENERAL ASPECTS FOR STATISTICAL ANALYSIS

#### 6.1. GENERAL METHODS

All patient data will be included in listings. All patients entered into the database will be included in patient data listings. The listings will be generally sorted by the study (and treatment) from which the patient was enrolled, Patient ID (and by visit and by time point, if applicable) within treatment group, unless specified otherwise.

All applicable data will be summarized by treatment group (CVT-301 DL1, CVT-301 DL2, CVT-301 overall) in tables, unless specified otherwise. Furthermore, selected summaries will be broken down into three groups as follows: patients who received CVT-301 in CVT-301-004 study, patients who received placebo in CVT-301-004 study and CVT-301 naïve patients (including CVT-301-005 observational arm patients) (referred to as “treatment/study group” in the SAP). The efficacy data from patients who were enrolled in the CVT-301-003 or CVT-301-009 study will be analyzed separately, as data listings. In addition, a patient disposition table will be provided for CVT-301-003 and CVT-301-009 patients. Where appropriate, data will be summarized by visit and/or time point in addition to treatment group. Unscheduled or repeat assessments will not be included in summary tables, but will be included in listings.

Continuous variables will be summarized using the number of observations (n), mean, SD, median, minimum, and maximum. Standard error of the mean (SEM) will also be provided for summaries of spirometry and efficacy endpoints, if relevant. The same number of decimal places as in the raw data will be presented when reporting minimum and maximum, 1 more decimal place than in the raw data will be presented when reporting mean and median, and 2 more decimal places than in the raw data will be presented when reporting SD and SEM.

Descriptive statistics for categorical/qualitative data will include frequency counts and percentages. The total number of patients in each treatment group/overall (N) will be used as the denominator for percent calculations, unless stated otherwise in the table shell. All percentages will be presented with one decimal point, unless specified otherwise. Percentages equal to 100 will be presented as 100% and percentages will not be presented for zero frequencies.

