## Statistical Analysis Plan

- Actual values and change from pre-dose to post-dose time points at TV1 by time point for each parameter
- Number and percentage of patients with PCS values at each applicable visit and time point for each standard vital sign parameter
- Number and percentage of patients with PCSC values at each applicable visit and time point for each standard vital sign parameter
- Number and percentage of patients with Orthostatic hypotension at each applicable visit

PCS and PCSC for standard vital sign will be identified as outlined in the following table.

Vital Sign	Units	Criteria for PCS Values (Actual values)		Criteria for PCSC values (Change from Baseline or pre-dose values *)	
		High	Low	increase	decrease
Pulse rate	bpm	>120	<40	100	50
Respiration Rate	brpm	>32	<8	50	NA
Systolic Blood Pressure (supine)	mmHg	>200	<85	60	20
Diastolic Blood pressure (supine)	mmHg	>120	<40		0.2x

\*Pre-dose values will be used for corresponding post-dose values assessment at TV1. Otherwise baseline values are used.

Orthostatic hypotension will be defined as a reduction in SBP of 20 mmHg or more, and/or a reduction in DBP of 10 mmHg or more, for the standing measurement compared to the supine/semi-supine measurement.

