## Statistical Analysis Plan

Table 14.3.4.2.2	Summary of Vital Signs: Actual Values and Change from Pre-dose at TV1 (Safety Population)
Table 14.3.4.2.3	Summary of Standard Vital Signs: PCS and PCSC Values by Treatment Group and Visit (Safety Population)
Table 14.3.4.2.4	Summary of Standard Vital Signs: PCS and PCSC Values by Scheduled Timepoint at TV1 (Safety Population)
Table 14.3.4.2.5	Standard Vital Signs: PCS and PCSC Values (Safety Population)
Table 14.3.4.2.6	Summary of Vital Signs: Orthostatic Hypotension by Treatment Group and Visit (Safety Population)
Table 14.3.4.2.7	Summary of Vital Signs: Orthostatic Hypotension by Scheduled Timepoint at TV1 (Safety Population)
Table 14.3.4.2.8	Orthostatic Vital Signs (Safety Population)
Table 14.3.4.3	12-Lead ECG: PCS and PCSC Criteria
Table 14.3.4.3.1	Summary of 12-Lead ECG: Actual Values and Change by Treatment Group and Visit (Safety Population)
Table 14.3.4.3.2	Summary of 12-Lead ECG: PCS and PCSC Values by Treatment Group and Visit (Safety Population)
Table 14.3.4.3.3	12-Lead Electrocardiogram (ECG): PCS and PCSC Values (All Available Population)
Table 14.3.4.4	Physical Examination by Treatment Group and Visit (Safety Population)
Table 14.3.4.5.1.1.1	Summary of Spirometry(Pulmonary Function Facility): Actual Values and Change from Baseline for FEV1 and FVC by Treatment Group and Visit (Safety Population)
Table 14.3.4.5.1.1.2	Summary of Spirometry(Pulmonary Function Facility): Actual Values and Change from Baseline for FEV1 and FVC by Treatment/Study and Visit (Safety Population)
Table 14.3.4.5.1.1.3	Summary of Spirometry (Pulmonary Function Facility): Actual Values and Change from Baseline for FEV1 by Treatment Group, Visit and Smoker Status (Safety Population)
Table 14.3.4.5.1.1.4	Summary of Spirometry (Pulmonary Function Facility): Actual Values and Change from Baseline for FEV1 by Treatment/Study, Visit and Smoker Status (Safety Population)
Table 14.3.4.5.1.2.1	Summary of Spirometry(Pulmonary Function Facility): Actual Values and Change from Baseline for FEV1 and FVC by Treatment Group and Visit Using Subset of Assessments Meeting the ATS Quality Criteria (Safety Population)
Table 14.3.4.5.1.2.2	Summary of Spirometry(Pulmonary Function Facility): Actual Values and Change from Baseline for FEV1 and FVC by Treatment/Study and Visit Using Subset of Assessments Meeting the ATS Quality Criteria (Safety Population)

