## Statistical Analysis Plan

Table 14.3.4.5.11.2	Summary of Spirometry(Neurology Office):Categories of Change from Baseline for FEV1 and FVC by Treatment/Study and Visit (Safety Population)
Table 14.3.4.5.11.3	Summary of Spirometry(Neurology Office):Categories of Change from Baseline for FEV1 by Treatment Group, Visit and Smoker Status (Safety Population)
Table 14.3.4.5.11.4	Summary of Spirometry(Neurology Office):Categories of Change from Baseline for FEV1 by Treatment/Study, Visit and Smoker Status(Safety Population)
Table 14.3.4.5.12.1	Summary of Spirometry(Neurology Office):Categories of Change from Baseline for FEV1/FVC by Treatment Group and Visit (Safety Population)
Table 14.3.4.5.12.2	Summary of Spirometry(Neurology Office):Categories of Change from Baseline for FEV1/FVC by Treatment/Study and Visit (Safety Population)
Table 14.3.4.5.13.1	Summary of Spirometry (Neurology Office): Actual Values and Change from Pre-dose for FEV1 and FVC at TV1 (Safety Population)
Table 14.3.4.5.13.2	Summary of Spirometry (Neurology Office): Actual Values and Change from Pre-dose for FEV1/FVC at TV1 (Safety Population)
Table 14.3.4.5.13.3	Summary of Spirometry (Neurology Office): Actual Values and Change from Pre-dose for FEV1 at TV1 by Smoker Status (Safety Population)
Table 14.3.4.5.14.1	Summary of Spirometry (Neurology Office): Categories of Percent Change from Pre-dose for FEV1, FVC at TV1 (Safety Population)
Table 14.3.4.5.14.2	Summary of Spirometry (Neurology Office): Categories of Percent Change from Pre-dose for FEV1/FVC at TV1 (Safety Population)
Table 14.3.4.5.14.3	Summary of Spirometry (Neurology Office): Categories of Percent Change from Pre-dose for FEV1 at TV1 by Smoker Status (Safety Population)
Table 14.3.4.6.1	Summary of Columbia-Suicide Severity Rating Scale (C-SSRS) by Treatment Group and Visit (Safety Population)
Table 14.3.4.6.2	Shift from Baseline in Columbia-Suicide Severity Rating Scale (C-SSRS) by Treatment Group and Visit (Safety Population)
Table 14.3.4.6.3	Summary of Self-Reported Columbia-Suicide Severity Rating Scale (C-SSRS) by Treatment Group and Visit (Safety Population)
Table 14.3.4.7	Summary of Epworth Sleepiness Scale Total Score: Actual Values and Change from Baseline by Treatment Group and Visit (Safety Population)

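### The TV1 pre-dose to post-dose lung and orthostatic tables pool first-ever CVT-301 doses with re-doses, so no planned summary table isolates the acute first-dose response

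*SAP*

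**What the plan says.** SAP 9.1, in the neurology-site summaries, plans "Actual values and change from pre-dose to post-dose time points for each parameter at TV1". SAP 9.6 plans "Actual values and change from pre-dose to post-dose time points at TV1 by time point for each parameter". Neither section splits these summaries by prior exposure to CVT-301; the only extra split is smoker status, for FEV1.

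The index in SAP 14 agrees. Nine tables carry the TV1 acute data:

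- Spirometry change: 14.3.4.5.13.1 to 13.3, for example "Summary of Spirometry (Neurology Office): Actual Values and Change from Pre-dose for FEV1 and FVC at TV1 (Safety Population".
- Spirometry categories of percent change: 14.3.4.5.14.1 to 14.3.
- Vital signs: 14.3.4.2.2, 14.3.4.2.4 and 14.3.4.2.7, the last being "Summary of Vital Signs: Orthostatic Hypotension by Scheduled Timepoint at TV1 (Safety Population".

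SAP 5.2 puts everyone enrolled in 004E who received at least one CVT-301 dose into the Safety Population, whatever their earlier exposure. SAP 6.1 does define a source-study grouping: "Furthermore, selected summaries will be broken down into three groups as follows", namely 004 CVT-301, 004 placebo, and naive (including the 005 observational arm). Under SAP 3.4.1, 004 patients enter only if they completed that study "without any safety issues that would preclude participation in this study according to the investigator".

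**The concern.** A post-dose reading at 004E TV1 means different things in different patients. In some it is the lung and blood-pressure response to a first inhalation. In others it follows about 12 weeks of use in people already known to have come through without a disqualifying problem. A table that mixes the two answers neither question cleanly.

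Elsewhere the SAP respects this distinction. SAP 6.2 sets baseline at first CVT-301 exposure, which for former 004 CVT-301 patients lies in study 004. SAP 9.4 counts treatment-emergent events from the first dose after that baseline. The visit-pooling table in SAP 8 marks this group's 004E baseline visit as not used. The TV1 acute tables do not follow the same logic.

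What is at stake is how well the report can describe the acute response of a new user, and how many true first doses support that description.

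**Working it through.** **Step 1. Who is in the TV1 tables** (SAP 3.4, 5.3 and 8; Protocol 7)

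| Source | What the 004E TV1 dose is |
|---|---|
| CVT-301-naive | First ever |
| 005 observational arm | First ever |
| 004 placebo | First ever |
| 004 CVT-301 | Re-dose at the same level, 1 to 14 days after the last 004 dose (longer with sponsor approval); 004 visits ran to Week 12 |
| 009 | Some had one earlier CVT-301 dose, some had placebo |
| 003 | Some had earlier CVT-301 followed by a gap, some had placebo |

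**Step 2. Whether another visit supplies the same data.** Protocol 10.1.3.2 and 10.1.3.3 schedule spirometry at 15, 30 and 60 minutes and standard and orthostatic vital signs at 20 and 60 minutes after the TV1 dose, for 004 roll-overs and new patients alike. After TV1, scheduled spirometry moves to the pulmonary laboratories (Protocol 11.1.6). In Appendices 6 to 10, vital signs at TV2 to TV6 are taken on arrival or before dosing. TV1 is therefore the only visit with scheduled post-dose spirometry and vital signs.

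**Step 3. Whether the SAP removes the re-dosed patients.** The not-used rule in SAP 8 is carried into SAP 9 only for the statistical analysis of spirometry; the other safety data are to be summarised in full. The re-dosed patients therefore stay in the nine descriptive tables. The neurology-office change, threshold and category tables do have treatment/study versions (14.3.4.5.6.2, 7.2, 8.2, 11.2 and 12.2). The TV1 pre/post tables have none.

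**Step 4. Size.** The plan gives no figure to reproduce: SAP 3.5 says the 390 planned patients do not rest on a formal calculation, and the mix by source study is not stated. Let f be the re-dosed share (assumed 20% to 60%) and r the re-dose response as a fraction of the first-dose response (unknown).

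- Share of the first-dose mean effect that survives pooling: (1 − f) + f × r.
- With zero events, the exact one-sided 95% upper bound on the event rate: 1 − 0.05^(1/n).

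| f | First-ever n of 390 | Kept if r = 0 | Kept if r = 0.5 | Kept if r = 1 | Bound, first-ever only |
|---|---|---|---|---|---|
| 20% | 312 | 80% | 90% | 100% | 0.96% |
| 40% | 234 | 60% | 80% | 100% | 1.27% |
| 60% | 156 | 40% | 70% | 100% | 1.90% |

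For all 390 pooled, the bound is 1 − 0.05^(1/390) = 0.77%.

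As an illustration with event rates, take 3% at first dose and 0.5% at re-dose, both assumed. The pooled rate is 0.8 × 3% + 0.2 × 0.5% = 2.50% at f = 20%, and 0.4 × 3% + 0.6 × 0.5% = 1.50% at f = 60%. If the two rates are equal, the pooled rate stays at 3%.

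The bound needs an assumption about f but none about r: a bound on the first-dose rate can draw only on first doses. Within the separate DL1 and DL2 columns, n is smaller and the bounds are wider.

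**The case against.** The strongest reply is that dilution has not been shown. Nothing in the documents says that re-dosed patients react less in the hour after inhalation; if they react equally, the pooled figures are unbiased. That stands. A reader might infer that the pooled tables necessarily understate new-user risk, but the documents support only the possibility. Selection of 004 completers makes it plausible, not established.

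A reader might also infer that these tables are the study's only view of acute safety. They are not. Adverse events are monitored at TV1 and through the supervised dosing at TV2 to TV6, where dyskinesia is also observed for 60 minutes. Several treatment-emergent event tables are planned by treatment/study group, including time to first onset. Patients who meet the TV1 spirometry alert criteria are reviewed individually. Table 14.3.4.5.9 displays low ratios and falls from pre-dose at the neurology sites, and the listings are generally sorted by source study, so the data can be separated by hand. What remains is narrower: no planned summary table gives the first-dose lung and orthostatic response separately.

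Three further replies deserve weight. SAP 6.1 promises the split only for selected summaries, and no vital-sign table has it, so for blood pressure the omission is uniform. No objective names the acute first-dose response; pulmonary safety is to be characterised over 12 or 14 months. And the SAP often uses TV1 as a synonym for baseline. If TV1 meant study 004 TV1 for former 004 CVT-301 patients, the pooling would vanish. That is not the plain reading: SAP 3.8 times visits from 004E TV1, and the footnote in SAP 9.6 separates TV1 pre-dose values from baseline. The text should still settle it.

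**Conclusion.** The pooling is real on the plain reading of SAP 9.1, 9.6 and the table index. It has two consequences of different strength. The number of first-ever doses behind the acute tables is overstated whenever any re-dosed patients are included: with zero events, a 0.77% bound where 0.96% to 1.90% would apply, given 390 treated patients and an assumed re-dosed share of 20% to 60%. Understatement of the response itself is possible but unquantified, from none at all upward, because neither the mix nor the re-dose response is documented.

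A reader might take this as an error in the primary analysis. It is not: that analysis concerns change in spirometry over the study, with baseline set at first CVT-301 exposure. This is a worthwhile and inexpensive improvement to descriptive safety tables.

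**What to change.** In SAP 9.1 and 9.6:

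1. State that TV1 in the pre-dose to post-dose summaries means 004E TV1.
2. Present the nine tables by prior exposure within DL1 and DL2. Make first-ever-exposed patients (naive, 005 observational arm, 004 placebo) the main acute display, and put former 004 CVT-301 patients in a separate column.
3. Show 003 and 009 roll-overs separately, because some had earlier doses and the three-group split in SAP 6.1 has no place for them.
4. Complete the SAP 9.1 fallback for a missing TV1 pre-dose spirometry value. It refers to the first dose without naming the drug or study, so for former 004 CVT-301 patients it could reach back to before study 004.

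The cost is a few sentences and some extra columns in nine tables, with smaller n per column. No new data are needed.

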### 9.2. EXTENT OF EXPOSURE

The following information will be summarized by treatment group and overall:

- The number of patients with dose change
- Duration of exposure to CVT-301 inhalations (days)
- Total exposure to CVT-301 inhalation, expressed as person years (sum of exposure to CVT-301 inhalations over all patients, classified by treatment group)
- Total number of doses and capsules taken, by visit and overall. Average number of daily doses and number of capsules, by visit and overall
- Proportion of days with 5, 4, 3, 2, 1 or 0 doses administered
- Proportion of patients using 5, 4, 3, 2, 1 or 0 doses/day at least once

In addition, these in-clinic data will be summarized by treatment group and visit:

## Statistical Analysis Plan

- Standard morning dose of LD-containing medications to in-clinic OFF (mins)
- In-clinic OFF to start of study drug inhalation (mins)
- Standard morning dose of LD-containing medications to start of study drug inhalation (mins)
- Duration of study drug inhalation (mins), calculated as (Completion time of last inhalation - Time of start of first capsule inhalation).

Furthermore, the distribution of time of intake of study medication (00:00 - 00:30, 00:30 - 01:00, ...) as percentage of the total number of study medication intakes will be displayed during the whole treatment period. This data will be collected on the Inhaled Dosing Log.

In addition, all the data will be broken down by treatment/study group. All study drug data will be listed. A listing will also be provided to show how many times each patient will take study drug and the capsules taken for each day.

### 9.3. TREATMENT COMPLIANCE

Patients will be instructed to administer inhaled study drug up to 5 times each day during the treatment period. In-clinic administration of study drug will be supervised by study personnel, and at-home diary data will be reviewed to ensure patient compliance. Since there are no fixed scheduled doses for each day, compliance will not be calculated for this study; alternatively, study drug use will be evaluated based on the inhaled medication treatment log by summarizing the proportion of days with >5, 5, 4, 3, 2, 1 or 0 doses administered.

### 9.4. ADVERSE EVENTS

All AEs will be coded using the MedDRA version 17.0.

Treatment-emergent adverse events (TEAEs) are defined as all AEs that start after the patient receives the first dose of CVT-301 after the relevant baseline (see Section 6.2 for the definition of baseline). Events will be classified as drug-related if the AE is classified as possibly, probably, or definitely related to study drug.

Events with a missing start time, but with a start date equal to the date of first dose of study drug will be considered treatment-emergent. If the AE start date is incomplete, then it will be imputed as follows for the purpose of determining TEAE:

- If the start date is completely missing, the start date will be equal to the first dose date. However, if the stop date is not missing and is before the first dose date, then the stop date will be used instead.

